**Functional Neuroimaging (fMRI):**

Magnetic resonance (MR) is a technique that uses magnetism and radio waves, not x-rays, to take pictures and measure chemicals of various parts of the body. The United States Food and Drug Administration (FDA) has set guidelines for magnet strength and exposure to radio waves, and we carefully observe those guidelines. Those who participate will be watched closely throughout the MR study. Some people may feel uncomfortable or anxious. If this happens to the patient, he/she may ask to stop the study at any time and we will take you out of the MR scanner. On rare occasions, some people might feel dizzy, get an upset stomach, have a metallic taste or feel tingling sensations or muscle twitches. These sensations usually go away quickly but we will instruct the patient to please tell the research staff if this occurs. There are some risks with an MR study for certain people. If a person has a pacemaker or some metal objects inside your body, he/she may not be in this study because the strong magnets in the MR scanner might harm them. Another risk is the possibility of metal objects being pulled into the magnet and hitting a participant. To reduce this risk, we require that all people involved with the study remove all metal from their clothing and all metal objects from their pockets. We also ask all people involved with the study to walk through a detector designed to detect metal objects. It is important to know that no metal can be brought into the magnet room at any time. Also, once a participant is in the magnet, the door to the room will be closed so that no one from outside accidentally goes near the magnet. We will make sure the participants read and answer very carefully the questions on the MR Safety Questionnaire related to their personal safety. We will ask each participant to take a moment and be sure that they have read the MR Safety Questionnaire and be sure to tell us any information they think might be important.

This MR study is for research purposes only and is not in any way a clinical examination. The scans performed in this study are not designed to find abnormalities. The primary investigator, the lab, the MR technologist, and the Magnetic Resonance Research Center are not qualified to interpret the MR scans and are not responsible for providing a diagnostic evaluation of the images. However, hi-resolution de-identified structural images may be shared with referring clinicians if requested for select patients to rule out gross anatomical markers or findings. Moreover, if a worrisome finding is seen on a scan, a radiologist or another physician will be asked to review the relevant images. Based on his or her recommendation (if any), the primary investigator or consulting physician will contact the participant, inform them of the finding, and recommend that they seek medical advice as a precautionary measure. The decision for additional examination or treatment would lie solely with the participant and their physician. The investigators, the consulting physician, the Magnetic Resonance Research Center, and Yale University are not responsible for any examination or treatment that they receive based on these findings.

**Genetic Samples:**

Donation of 30 ml of blood for genetics studies will be part of every Informed Consent document. Subjects will be informed of possible risks and benefits of participation in genetics research will be informed of the potential genomewide scope of the genotyping effort, and will

be informed that their DNA samples will be retained indefinitely (banked). A Certificate of Confidentiality from NIAAA has been obtained to further protect the confidentiality of this information.

**9. Minimizing Risks:** Describe the manner in which the above-mentioned risks will be minimized.

**Saracatinib:**

Effective screening will exclude all subjects who would be at greater risk for complications because of medical, neurological or psychiatric illnesses or who have any of the other exclusion criteria (described above). Individuals currently dependent on other drugs will be screened out. Subjects maintained on study medication will be issued "keyed" cards which allow health professionals to break the double blind by calling the Yale-New Haven pharmacy switchboard, which answers 24 hours a day. Subjects will also be monitored daily for frequency and severity of adverse events using the SAFTEE. These adverse events will be reviewed daily by the study physician, [name] or the APRN, [name]. We will also repeat blood draws for routine CBC tests and hepatic, kidney and thyroid function tests at the end of the treatment period and at one week follow up (51cc).

The Investigator's Brochure states that Saracatinib should not be administered to pregnant or breast-feeding women and it is recommended that non-childbearing status should be confirmed by a negative pregnancy test before administration of Saracatinib in women of childbearing potential. Conception must be avoided during maternal or paternal exposure to Saracatinib.

Therefore, the following precautions will be taken for women: 1) Urine pregnancy tests will be performed at intake, prior to starting the medication, and on the day of the alcohol self administration sessions. Pregnant or nursing women will be excluded from participation and encouraged to seek advice about the risk of heavy drinking, encouraged to seek alcohol treatment, and, if interested, referred to other cessation programs. 2) Women and men must agree to use a reliable method of birth control while they are in the study. Each female subject will be asked to alert the principal investigator if she departs from her birth control plans or if, in spite of adherence to these plans, she thinks she might be pregnant. Each male subject will be asked to alert the principal investigator if he departs from his birth control plans or if, in spite of adherence to these plans, he thinks his partner might be pregnant.

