### **Follow up interview**

Subjects will participate in a 1-week follow-up appt. during which drinking over the past week and remaining adverse events will be monitored and a **blood sample to for safety laboratory tests will be obtained** (50cc). A brief motivational intervention will be provided by a licensed clinical psychologist or licensed social worker to encourage subjects to address their alcohol problem and an immediate referral to treatment will be made if they are interested. Even though participants are not seeking treatment for their drinking, we feel that their presence in the hospital provides a “teaching moment” to address their drinking behavior (Sinha et al., 1997). Subjects will also participate in a 1-month follow up during which information about their drinking since their prior appointment will be assessed.

**Motivational intervention:** A brief motivational intervention will be provided at the one-week follow-up to encourage the subject to address their alcohol problem. For Study 1, this session will be audiotaped if the subject agrees to sign consent for audiotaping. Tapes will only be used for training purposes and will be identified by code numbers and erased within 7 years of study completion. Even though the subjects participating in this study are not seeking treatment for their drinking, we feel that participation in this study is an opportunity to address their heavy drinking behavior. This brief motivational interview is based on the principles of Miller's Motivational Enhancement Therapy (MET) [133]. We will provide subjects with personalized feedback regarding their physical exam and laboratory findings, and on the influence of drinking on their health. We will also review with them the potential benefits of quitting drinking. We have found that similar brief advice resulted in decreases in alcohol drinking behavior and increased motivation to quit drinking [132]. If interested, an immediate referral to treatment will be made. Also, subjects will also be given the option of participating in one of our alcohol treatment studies.

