***Blood and Urine Collections:***

Screening blood and urine collections are performed primarily as safeguards to subjects and should add no risks other than those normally associated with these procedures. Subjects will have approximately 50 cc of blood drawn at the intake, second self-administration, and at one week follow up appointments to determine liver and kidney functioning. In addition, a total of 10 cc of blood will be drawn at the lab sessions to determine alcohol levels. Therefore, the total amount of blood drawn during the study (160 ml) is well within the HIC guidelines of 450 cc

within eight research weeks, and the blood loss poses minimal risk in healthy subjects. We will advise subjects against donating blood for six weeks following study participation.

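### The last explicitly scheduled pregnancy test falls on the last dosing day, too early to show almost any conception during exposure; a urine test at the one-month appointment would be a cheap, optional addition

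*Combined protocol and SAP*

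**What the plan says.** Section V, item 9 (Minimizing Risks, under Saracatinib) sets the schedule: "Urine pregnancy tests will be performed at intake, prior to starting the medication, and on the day of the alcohol self administration sessions". The Research Plan puts the second drinking session on the last medication day, and the Medication Treatment Period section has the eighth dose taken on arrival that day.

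The same part of item 9 says "Conception must be avoided during maternal or paternal exposure to Saracatinib" and "Women and men must agree to use a reliable method of birth control while they are in the study". Participants are also asked to tell the principal investigator of a lapse in birth control or a suspected pregnancy, their own or a partner's. The risk section (Section V, item 8) reports that animal studies suggest fetal eye defects.

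After dosing, item 9 names repeat CBC and "hepatic, kidney and thyroid function tests at the end of the treatment period and at one week follow up". The Follow up interview section says that at one week a "blood sample to for safety laboratory tests will be obtained", without listing the tests. For the last appointment it says: "Subjects will also participate in a 1-month follow up during which information about their drinking since their prior appointment will be assessed". The Research Plan offers an optional fMRI there.

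**The concern.** The protocol's rule covers exposure, which outlasts dosing. The explicit testing schedule ends with the last dose. A test on that day can find a pregnancy that began before treatment, but a conception during treatment is generally too recent to show, and one during washout has not yet happened.

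If contraception fails in that window, detection depends on the woman suspecting a pregnancy and reporting it. Given the fetal risk that the protocol itself names, and a population of heavy drinkers, it would help to find such a pregnancy while staff still see the participant and can advise her. The stake is individual safety; no aim, estimate or error rate is affected.

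**Working it through.** The plan gives no figure of its own to reproduce, so the check is one of timing.

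**Inputs from the protocol.** The half-life is about 40 hours (Justification for length of treatment phase). The session-day dose is the eighth (Medication Treatment Period). The Research Plan allows 7 to 10 outpatient days, so on the longest reading the session falls on day 11. The 8-dose reading is the better supported, since Section VI.A, item 5 caps placebo at 8 days. Follow-up is at one week and one month.

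**Assumptions, not in the protocol.** Washout takes 4, 5 or 7 half-lives. A urine test turns positive 10 or 14 days after conception, with 21 days as a slow case. The one-week visit is 7 or 8 days after the session, and the one-month visit 28 or 30 days after.

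**Exposure window.** Washout is n × 40/24 days: 6.7, 8.3 and 11.7 days for n = 4, 5 and 7. With the last dose on day 8, exposure ends on day 14.7, 16.3 or 19.7 (14, 16 or 19 whole days). With the last dose on day 11, it ends on day 17.7, 19.3 or 22.7 (17, 19 or 22 whole days).

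**Coverage.** A conception on day d shows at a test on day T with lag L if T − d ≥ L, so the days covered are 1 to T − L. Each cell gives the days covered out of the exposure days.

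| Test | 8 doses, lag 10–14 | 11 doses, lag 10–14 |
|---|---|---|
| Session day (T = 8; 11) | 0 of 14–19 | 0–1 of 17–22 |
| Morning after, if done (T = 9; 12) | 0 of 14–19 | 0–2 of 17–22 |
| One week, if done (T = 15–16; 18–19) | 1–6 of 14–19 | 4–9 of 17–22 |
| One month (T = 36, 38; 39, 41) | all | all |

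The one-week row runs from 1/19 = 5% to 9/17 = 53%. Of the 2 schedules × 3 washouts × 2 test days × 2 lags = 24 combinations, only 9/17 exceeds half.

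**Slow lag at one month.** With L = 21 and T = 36, days 1 to 15 are covered: 15 of 16 (94%) at five half-lives and 15 of 19 (79%) at seven. The lowest value on the 11-dose schedule is T = 39, covering 18 of 22 (82%). The minimum is 79%.

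**Expected events.** The protocol gives no sex split. Assume 13 to 20 women among the 40 on active drug and 1% to 10% contraceptive failure a year. Expected events = women × exposure days/365 × yearly failure.
- Low: 13 × 13.7/365 × 0.01 = 0.005.
- High: 20 × 21.7/365 × 0.10 = 0.12.
- High with 8 doses: 20 × 18.7/365 × 0.10 = 0.10.

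**The case against.** The strongest reply is that nothing in the plan is wrong. A test before first dosing is scheduled, as the Investigator's Brochure recommends. Birth control is required of both sexes while in the study, refusal is an exclusion criterion, and the study runs to the one-month follow-up, past the longest washout assumed here. Self-report continues, adverse events are asked about at follow-ups, and participants carry cards that "allow health professionals to break the double blind by calling" the pharmacy switchboard. A late test cannot prevent exposure, and the expected number of events is far below one. All of this stands, and it is why the point is optional.

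A second reply is that later tests may already be intended. The section on assessments during and after the choice periods repeats all baseline laboratory tests the morning after the second session, and the baseline examination includes pregnancy tests. The one-week safety tests are not itemised there. Both readings are possible, although item 9 names only CBC, hepatic, kidney and thyroid tests for those draws. Even if both pregnancy tests were done, the coverage table shows that the first would miss nearly all of the window and the second generally more than half.

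A reader might infer from Blood and Urine Collections, which gives liver and kidney functioning as the purpose of the draws, that pregnancy testing was deliberately left out later. The text does not support that. The same sentence covers the intake draw, which the eligibility section links to pregnancy tests, so the stated purpose is incomplete.

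A reader might also infer that the plan has no route for reporting an exposed pregnancy. The documents do not establish this. The Data and Safety Monitoring Plan counts a birth defect as a serious adverse event, and the consent pages, which may say more, are not in the supplied text.

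**Conclusion.** The point holds as an optional safety improvement. The last explicitly scheduled pregnancy test would show almost no conception during dosing or washout. A one-month urine test would probably detect one in a female participant: all exposure days under a 10 to 14 day lag, and at least 79% under 21 days.

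It is tempting to say that the test would certainly detect every exposed conception. That depends on a lag the protocol does not give, and on when the month starts, which it does not say. Counting from the one-week visit would only improve coverage. It is equally tempting to call this a breach of the protocol's own contraception rule. It is not: the rule concerns prevention, which the plan addresses.

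The result rests on the stated half-life and on the assumed washout, lag, sex split and failure rate. The yield is low, about 0.005 to 0.12 expected events. Partners of male participants would still be covered only by self-report.

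**What to change.** In the Follow up interview section and in Section V, item 9 (Saracatinib), add: *A urine pregnancy test will be performed at the one-month follow-up for women of childbearing potential.*

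The cost is that sentence in two places and one urine dipstick per woman, with no extra blood and no new visit. The one-month appointment is already scheduled and paid for (Section X, item 2). That it takes place in person is inferred from the payment and the optional fMRI, so the team should confirm it. The downside is that very few positive results are to be expected.

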**Confidentiality Safeguards**

Right to privacy for participation in this research will be protected through anonymous coding of data and proper storage of research records. A list of numbers and the corresponding names will be maintained by the Project Director. Access will be limited to the PI and her designates involved in the study. Data from CTNA projects will be maintained by the Data Management and Biostatistics Component (DMBC) and/or Investigator. Data will be available on request after the completion of analyses by the Investigators and after publication of results. Requests should be submitted to the Investigator with details about the type of information needed and plans for use. After review between the Requestor and Investigator, and approval by the Executive Committee, the agreed-upon list of files will be submitted to the DMBC for preparation and delivery to the Requestor.

A certificate of confidentiality has been obtained from the NIAAA, which will protect the confidentiality of all research records generated by this study. Other safeguards include screening by experienced professionals in order to ensure that the inclusion and exclusion criteria are met before patients are entered in the study, including physical exam and laboratory tests.

Subjects will be informed about possible risks from participating in genetics research. They will be informed that DNA will be stored indefinitely. They will be informed that genotyping (possibly extending to genomewide extent) will take place on their donated DNA. They will also be told that under some circumstances, it can be a risk for genetic information about to be known but that we will keep the results of the genetic testing confidential. We will not make any of our results available to them or add it to their medical records. If they want to know their risk of a genetic disease, we will refer them to a genetic counselor. Finally, they will also be informed that this genetic data may be subject to sharing with other investigators, and that if data are shared, it will be in anonymous form, that is, with no personal identifiers.

*Alcohol challenges*

The alcohol challenges will be conducted by personnel experienced in alcohol challenge research. We provide a number of safeguards to reduce the risk of physical injury by supervising all sessions and having subjects stay in a safe environment overnight. We also exclude subjects for whom physical or psychological problems contraindicate alcohol consumption. By selecting non-treatment-seeking subjects who are currently drinking heavily on a regular basis, we are not exposing subjects to alcohol consumption levels that differ from their normal drinking context. Although we have never had a subject chose to leave a session early, should a subject insist on leaving the research setting prematurely, we will provide transportation back to their residence. This contingency is explicitly addressed in the consent form. Clearly, subjects are free to discontinue the experiment at any time, although we would strongly encourage them to remain in the research setting until their blood alcohol level is below .02. Because subjects are not in treatment, participation in an alcohol challenge study will not interfere with efforts to achieve abstinence. At the end of the study, however, a potential benefit is that subjects will be provided with a professional evaluation and a motivational intervention to encourage them to seek treatment.

*Functional Neuroimaging (fMRI)*

Participants will be appropriately screened for metals as will all personnel who enter the room that contains the MRI scanner. This screening will involve a self-report questionnaire, an interview with a trained radiographer and assessment with a ferromagnetic metal detector. Subjects will also be monitored physiologically throughout the scanning session using pulse oximetry. Their heart rate and blood pressure will be monitored at all times while they are in the MRI scanner.

**10. Data and Safety Monitoring Plan:** Include an appropriate Data and Safety Monitoring Plan (DSMP) based on the investigator's risk assessment stated below. (Note: the HIC will make the final determination of the risk to subjects.) For more information, see the Instructions, page 24.

- a. What is the investigator's assessment of the overall risk level for subjects participating in this study? This protocol is a greater than minimal risk protocol and therefore requires a data safety and monitoring plan.
- b. If children are involved, what is the investigator's assessment of the overall risk level for the children participating in this study? N/A
- c. Include an appropriate Data and Safety Monitoring Plan. Examples of DSMPs are available here <http://www.yale.edu/hrpp/forms-templates/biomedical.html> for
  - i. Minimal risk ii.
  - Greater than minimal

**1) Plan for Grading Adverse Events and Attribution of Adverse Events**

Side effects/adverse experiences are collected on standardized forms, using the SAFTEE (Levine and Schooler, 1986). The SAFTEE includes 1) open-ended questions about any changes in physical or health problems, appearance, or activity level, and 2) yes/no questions on a specific list of symptoms (which correspond to anticipated adverse events associated with Saracatinib) for a specified time period. For each symptom reported on the SAFTEE a rater also records the date of onset, severity (minimal, mild, moderate, severe), whether it was drug-related, and action taken. The SAFTEE is administered at baseline, during the inpatient periods, and every other day during the outpatient treatment periods. We will monitor the number of patients experiencing symptoms and the severity of symptoms.

**2) Plans for unanticipated and anticipated serious adverse events reporting to the IRB/HIC, funding agency, and regulatory agency**

**2.a. Definition of Serious Adverse Events:** The FDA's definition of serious adverse events (21 CFR 312) will be used. SAEs include any untoward medical occurrence that at any dose results in death or the immediate risk of death, hospitalization or the prolonging of an existing hospitalization, persistent or significant disability/incapacity, or a congenital anomaly/birth defect (NIH Guide-6/11/99)

**2.b. Plans for reporting serious adverse events:** Adverse events that meet the criteria for a Serious Adverse Event will be reported to the IRB, MAC, and NIAAA within 24 hours by phone and in writing within 1 week.

**3) Plans for reporting non-serious anticipated and unanticipated adverse events**

The number of subjects (and percentage) reporting each anticipated adverse event would be reported on an annual basis to the IRB, MAC, and NIAAA as part of annual progress report (NIAAA) and annual reapproval (IRB). These will be reported for the overall sample and not by treatment condition in order to maintain the blind. However, if anticipated adverse events occur in greater magnitude or frequency than expected, then these will be reported to the IRB and NIAAA.

